7.4.3. Prevalent algorithms

The prevalent algorithm is used to establish the type of diabetes for prevalent cases. This algorithm displays use of data collected from the In-Person Visit Module. For prevalent cases for whom the In-Person Visit is not available, typology will proceed using data collected from the Core Form. (See Data Collection, Section 5, for descriptions)

Algorithm - Prevalent Cases – Information Available from In-Person Visit

[figure not shown]
- a. Type 1A diabetes will be established if any of the three DAA (GAD, IAA, and IA-2) are positive and a fasting C-peptide < 0.8 ng/ml (see appendix VII).
- b. Type 1 diabetes will be established if all DAA are negative and a fasting C-peptide < 0.8 ng/ml;
- c. Type 2 diabetes will be established if *all* DAA titers are negative and a fasting C-peptide is ≥ 3.7 ng/ml.
- d. Hybrid diabetes is established if any DAA is positive and fasting C-peptide ≥ 3.7 ng/ml.
- e. DAA positive patients ≥ 8 years of age at their baseline examination who have a fasting C-peptide ≥ 0.8 ng/ml and < 3.7 ng/ml will undergo a single SCP test. These data will be used to type the participants in the following manner:
 - i. The clinical and SCP data will be compared to the same data generated in the sub-groups of the incident cases classified as type 1A, hybrid diabetes and type 2.

[figure not shown]
- ii. The clinical and SCP data will be compared to the same data generated in the prevalent cases classified as hybrid diabetes and prevalent cases that are untypeable.
- f. DAA negative patients ≥ 8 years of age at their baseline examination who have a fasting C-peptide ≥ 0.8 ng/ml and < 3.7 ng/ml will undergo a single SCP test. These data will be used to type the participants in the following manner:
- i. The SCP data will be compared to the same data generated in the sub-groups of the incident cases classified as type 1A diabetes and type 2 diabetes. When the data is comparable to the sub-groups, a classification of type 1 or type 2 will be made.
 - ii. In the remaining participants who cannot be classified by the method described in ‘i’ (above), the clinical definitions of the types of diabetes found in appendix VI will be used to classify participants as type 1 and type 2 diabetes.
 - iii. The remaining participants who cannot be classified by the method described in ‘ii’ (above) will be classified as untypeable.

Algorithm- Prevalent cases – Information Available from In-Person Visit Not Available

Prevalent cases for which the In-person Module is not available, information may be available from the Core Form (including the limited medical record review for typology, for prevalent cases; see Section 5 - Data Collection). The following information will be obtained: 1) DAA and plasma C-peptide tests and the laboratory at which these tests were performed, and 2) limited clinical data.

8.1 STATISTICAL ANALYSES

8.1.1 Estimation of prevalence and incidence

The methods for determining the numerator and denominators for estimates of prevalence and incidence are described in section 4.1. These data allow estimates of prevalence and incidence for each of the six clinical sites. In addition, these estimates will be calculated by Type (1, 2, hybrids), race/ethnicity categories (NHW, AA, Hispanic, Asian, PI, NA), gender, and age groups (10 year, 5 year, and single year). National estimates of prevalence and incidence will be achieved by using age, sex, and race/ethnicity adjusted estimates, adjusted to the distribution of age, sex, and race/ethnicity for the 2000 US national population. Completeness of ascertainment will be assessed by examining the rates of concordant and discordant detection among ascertainment modes. When more than two modes are used, log-linear models will be fitted to assess the dependency between complementary modes of ascertainment²⁸.

8.1.2 Comparison of methods for classification of diabetes type

The accuracy of evaluating different approaches to the classification of diabetes type for prevalent and incident cases will be based on misclassification ratios. The number of misclassifications will be used to estimate the proportion of false positives, false negatives, sensitivity and specificity. In evaluation of potential measures that are continuous or ordinal, receiver operator curves (ROC) will be used to evaluate and test the usefulness of the diagnostic measure.

8.1.3 Comparison of type 1 and type 2 and other types of diabetes

Patient characteristics and clinical presentation will be compared between types of diabetes. These factors include measures of clinical presentation, risk factors for micro- and macrovascular disease complications, health care utilization, and quality of life. Comparisons between the disease types will be made by Chi-square tests for categorical measures, Wilcoxon rank-sum tests for ordinal measures, and analysis of variance for continuous measures. Analyses will be performed separately for prevalent and incident cases. Analysis of covariance procedures will be used to compare risk factors between types of diabetes adjusting for possible confounders (e.g. age, sex, and race/ethnicity).

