1.2. PRIMARY AIMS

- a) Estimate the population prevalence and incidence of type 1, type 2, and other types (or hybrids) of diabetes rates overall and by age, gender and ethnicity.
- b) Develop efficient and practical approaches to classification of diabetes type for prevalent and incident cases.
- c) Describe and compare clinical presentation and course of type 1, type 2, and other types (or hybrids) of diabetes

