7.2. METHOD OF TYPOLOGY

Background

The report of the American Diabetes Association (ADA) Expert Committee on the Diagnosis and Classification of Diabetes Mellitus published in *Diabetes Care*³² serves as the basis of definitions of the types of diabetes used in this study. The fundamental principle of the classification scheme is that definitions of diabetes types reflect pathogenesis. As a result, diabetes autoantibodies (DAA) and C-peptide information will be collected on incident and prevalent cases as the primary method of classification in this study. However, due to gaps in knowledge of diabetes pathophysiology, heterogeneity of diabetes, and that assignment of type depends on the circumstances at diagnosis, many patients are not easily categorized or typeable. To combat these limitations, the following two approaches will be used.

- a. Participants, who, at initial evaluation, cannot be classified by pathogenic criteria, will be followed longitudinally to explore the evolution of diabetes and classification will be reassigned if etiology and pathogenesis becomes clear.
- b. At study completion, clinical characteristics identified in those participants classified based on pathophysiological characteristics of diabetes type will be used to “redefine” clinical definitions of diabetes type. These “redefined” clinical definitions will be used to re-type patients who have only clinical data available.

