7.3. DEFINITIONS OF TERMS USED FOR TYPOLOGY

7.3.1. **Type 1 diabetes**

The progressive destruction of the beta cells leading to an absolute deficiency of insulin (see insulinopenia below) that results in diabetes.

Type 1 diabetes will be established if all diabetes autoantibodies (DAA – see autoimmunity below) are negative and any of the following are present:

- a. Fasting C-peptide < 0.8 ng/ml;

Or

- b. Diagnosis of diabetes was made when the subject was < 10 years of age with a weight < the 25th percentile for chronological age or BMI < 50th percentile for chronological age;

Or

- c. Duration of diabetes > 1 year and if daily administration of insulin is stopped it results in DKA.

7.3.2. **Type 1A diabetes (general)**

The autoimmune destruction of the beta cells leading to an absolute deficiency of insulin resulting in diabetes.

7.3.3. **Type 1A diabetes (biochemical)**

The presence, in plasma, of any specific diabetes autoantibody and a fasting C-peptide < 3.7 ng/ml. These markers include antibodies to glutamic acid decarboxylase (GAD), IA-2, and insulin autoantibodies (IAA) measured by radioassay and cytoplasmic islet cell antibodies measured by immunofluorescence (ICA). The frequency of the presence of immune markers decreases with increased duration of disease with only 65% of Type 1A patients having one or more positive immune markers with duration of disease of 10 years^{33,34}.

7.3.4. **Type 2 diabetes (general)**

The presence of insulin resistance (see insulin resistance) and beta cell dysfunction resulting in diabetes. Type 2 diabetes will be established if one of the following exists:

- a. Duration of diabetes > 1 year and no insulin therapy for > 1 month without an episode of diabetic ketoacidosis

Or

- b. Duration of diabetes > 6 months and never treated with insulin.

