7.4.2. Incident algorithms

The incident algorithm will be used to establish type of diabetes for incident cases. This algorithm displays use of data collected from the In-Person Visit Module. For incident cases for whom the In-Person Visit is not available, typology will proceed using data collected from the Medical Record Module or the Core Form. (See Data Collection, Section 5, for descriptions)

Algorithm - Incident cases– Information Available from In-Person Visit

- a. Type 1A diabetes will be established if any of the three DAA (GAD, IAA, and IA-2) is positive and the fasting C-peptide is < 3.7 ng/ml.
- b. Type 2 diabetes will be established if the DAA titers are all negative and the fasting C-peptide is ≥ 3.7 ng/ml.
- c. Hybrid diabetes is established if any DAA are positive and fasting C-peptide is ≥ 3.7 ng/ml.
- d. DAA negative participants ≥ 8 years of age at their baseline examination who have a fasting C-peptide concentration < 3.7 ng/ml will undergo additional DAA and SCP testing as described in Section 5 – Data Collection. These data will be used to classify participants in the following manner.
 - i. If any subsequent DAA become positive, a classification of ‘type 1A diabetes’ will be made.
 - ii. If all subsequent DAA remain negative and one or more fasting C-peptide concentrations < 3.7 ng/ml, classification will be made in the following manner. Clinical characteristics and SCP data collected over time will be compared to the same data generated in the sub-group of the incident cases classified as type 1A or all incident cases classified as type 2 diabetes. Where the data matches these groups, a classification of type 1 or type 2 will be made.
 - iii. In remaining participants who cannot be classified by the method described in ‘ii’ (above), clinical definitions of the types of diabetes found in appendix VI will be used to classify participants as type 1 and type 2 diabetes.

- iv. The remaining participants who cannot be classified by the method described in 'iii' (above) will be classified as untypeable.

Algorithm - Incident cases – Information from In-Person Visit Not Available

Among incident cases for which the In-person Module is not available, information may be available from the Core Form and/or Medical Record review. The following information will be obtained: 1) DAA and plasma C-peptide tests and the laboratory at which these tests were performed, and 2) limited clinical data.

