8.1.4 Estimation of the clinical course

The clinical course of incident subjects will be estimated from longitudinal data collected once per year. The natural history and comparison between disease types will be estimated and tested using repeated measures analysis of covariance and mixed models³⁷. Maximum likelihood will be used to fit these models. This allows increased precision and minimizes bias associated with varying lengths of follow-up among participants.

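### Some cases are typed from onset age, weight/BMI, insulin use and DKA, and the types are then compared on those same features, so those differences are partly built in

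*Protocol*

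**What the plan says.** **The aim.** Primary aim (c) in Section 1.2 is: "Describe and compare clinical presentation and course of type 1, type 2, and other types (or hybrids) of diabetes".

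**How type is assigned.** Section 7 starts with diabetes autoantibodies (DAA) and fasting C-peptide. Where these do not settle the type, clinical information enters in several places:

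- Section 7.4.2, step d.ii (incident, DAA-negative, aged 8 or over, fasting C-peptide below 3.7 ng/ml): "Clinical characteristics and SCP data collected over time will be compared to the same data generated in the sub-group of the incident cases" already typed. SCP is the stimulated C-peptide test.
- Section 7.4.2, step d.iii, for incident cases still unresolved: "clinical definitions of the types of diabetes found in appendix VI will be used to classify participants as type 1 and type 2 diabetes". Section 7.4.3, step f.ii, has the same rule for DAA-negative prevalent cases that SCP does not resolve.
- Section 7.4.3, step e, compares clinical and SCP data for DAA-positive prevalent cases with C-peptide from 0.8 to below 3.7.
- Section 7.2(b): at study end, redefined "clinical definitions will be used to re-type patients who have only clinical data available".

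**What the clinical definitions contain.** In Section 7.3.1 and Appendix VI, clinical type 1 rests on onset before age 10 with low weight or low BMI for age. Section 7.3.1 adds DKA when insulin is stopped. Type 2 rests on course: "Duration of diabetes > 1 year and no insulin therapy for > 1 month without an episode of diabetic ketoacidosis", or never having been treated with insulin after more than six months.

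**How types are compared.** Section 8.1.3: "Patient characteristics and clinical presentation will be compared between types of diabetes". It continues: "These factors include measures of clinical presentation, risk factors for micro- and macrovascular disease complications, health care utilization, and quality of life". Section 8.1.4, for incident cases: "The natural history and comparison between disease types will be estimated and tested using repeated measures analysis of covariance and mixed models". Neither section distinguishes cases by the basis of their type.

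**The concern.** A case called type 1 because onset was before age 10 and BMI was low contributes an early onset and a low BMI to the type 1 mean by construction. A case called type 2 because it stayed off insulin without DKA contributes exactly that to the type 2 course. For such cases the comparison returns the definition and carries no information on how the types differ.

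At stake are the estimates for aim (c) on onset age, weight/BMI, insulin use and DKA, and on C-peptide course where SCP served for typing. Some of these features may truly differ between types; the harm there is an exaggerated estimate. For correlated risk factors a null is plausible, because Section 2.3 says it is unclear whether complication risk factors differ by type.

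The covariance adjustment in 8.1.3 does not help. Onset age is itself a typing rule, and selection on BMI acts on the compared variable directly.

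**Working it through.** **1. The plan's own figure.** Table 6-3 gives, overall, 3,736 type 1 and 1,048 type 2 cases and a detectable difference of 0.10 SD (80% power) or 0.11 SD (90%). The group sizes are 0.75 × 4,981 and 0.75 × 1,397 (Appendix V, Tables V-1 and V-2, with 75% participation). No alpha is stated; two-sided 0.05 is assumed.

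- SE = √(1/3,736 + 1/1,048) = 0.0350 SD
- 80% power: (1.960 + 0.842) × 0.0350 = 0.098 SD
- 90% power: (1.960 + 1.282) × 0.0350 = 0.113 SD

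The table reproduces. It concerns prevalent cases and measures that are not typing variables, so it serves here for precision only, not as a yardstick for the bias.

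**2. Built-in BMI difference, simple case.** Assume no true BMI difference and BMI as a standard normal z-score. Let a share f of the type 1 group be typed by the below-median BMI rule. The mean of a standard normal below its median is −√(2/π) = −0.798, so the built-in difference is 0.798 × f SD. The last column is the chance of a significant result at the group sizes of Table 6-3.

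| f (assumed) | Built-in difference (SD) | False significant result |
|---|---|---|
| 5% | 0.04 | 21% |
| 10% | 0.08 | 63% |
| 20% | 0.16 | 99.5% |

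**3. Correlates.** If another measure correlates r with BMI and the relation is linear, its built-in difference is r times the above. At an assumed r = 0.3 this is 0.3 × 0.04 = 0.012 SD at f = 5% and 0.3 × 0.08 = 0.024 SD at f = 10%.

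**4. Closer to the protocol's rules.** A null simulation (4,784 cases, 1,000 runs per setting) left a share g of all cases unresolved by biochemistry. It typed them by onset before 10 with low BMI (type 1) or by being off insulin (type 2), and left the rest untypeable. Assumptions: onset before 10 in 30–50% of cases, off insulin in 20%.

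| g (assumed) | Built-in BMI difference (SD) | Type I error, BMI | Built-in gap in no insulin use (percentage points) |
|---|---|---|---|
| 0 | about 0 | 5.3–5.9% | about 0 |
| 5% | 0.012–0.022 | 6–10% | about 3 |
| 10% | 0.027–0.043 | 12–21% | about 6 |
| 20% | 0.061–0.097 | 41–77% | 12–13 |

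Here g is a share of all cases and f a share of the type 1 group. Many unresolved cases end untypeable, so the same percentage gives a smaller bias than in step 2.

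**5. Cost of restriction.** Leaving out a share x of cases multiplies the detectable difference by 1/√(1 − x): 0.098/√0.9 = 0.103 SD at 10%, and 0.098/√0.8 = 0.109 SD at 20%.

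**The case against.** The strongest reply is that the clinical rules are a fallback. DAA and C-peptide come first, the Appendix VI definitions mainly apply after SCP has failed, and cases meeting neither rule are left untypeable. For DAA-negative prevalent cases, the step before the fallback uses SCP alone. The incident fallback for type 1 is narrow, since it covers participants aged 8 or over at baseline while clinical type 1 needs onset before 10. All of this stands and limits the reach.

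Cases re-typed under 7.2(b) have clinical data only. They lack most visit-based outcomes, and they cannot enter 8.1.4, because Section 5.8 invites to follow-up only incident cases who had an initial examination. This also stands. They can still affect survey- and record-based presentation items, and the Initial Patient Survey collects age and body size at diagnosis, DKA and insulin use, which are the defining features.

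A reader might infer that every between-type comparison is invalid, or that only biochemically typed cases should form the main set for all outcomes. The documents do not support this. Utilization and quality of life are touched only indirectly. Biochemical type 2 requires C-peptide of at least 3.7 ng/ml, which the protocol sets above the 95th percentile of healthy adolescents. Incident steps a to c give no type to any DAA-negative case below that value. A biochemical-only main set would thus replace one selection with another and leave SCP-typed cases unplaced.

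Analysis sets and sensitivity analyses are commonly left to a SAP, so their absence alone would be no finding. Here, however, the typing rules and the unrestricted comparison are both written in the protocol, and together they produce the circularity.

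**Conclusion.** The concern holds for the defining features (onset age, weight/BMI, insulin use and DKA) and, more weakly, for their close correlates. Following Sections 7 and 8 as written builds part of those differences into the result.

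The size cannot be fixed from the documents. The protocol says many patients are not easily typed but gives no share typed clinically. The illustration of 0.04 SD at f = 5% and 0.08 SD at f = 10% assumes no true difference, a normal BMI z-score and typing on BMI alone; with an untypeable group the bias is smaller. Every value of f, g and r is an assumption.

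Two stronger readings go too far. One is that the bias should be judged against the 0.10 SD of Table 6-3; that figure concerns vascular, complication and utilization measures. The other is that the sensitivity and specificity in 8.1.2 are overstated. That would follow only if clinically typed cases served as the reference; 8.1.2 names none, and 7.2(b) derives its redefined clinical rules from cases classified on pathophysiology.

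**What to change.** 1. Record for each case the basis of its type: DAA and fasting C-peptide, SCP alone, clinical matching, or clinical rule.
2. In 8.1.3 and 8.1.4, test differences in onset age, weight/BMI, insulin use and DKA only among cases whose type used no clinical features (the first two categories). Report these features descriptively for clinically typed cases. Where SCP was used for typing, treat C-peptide course the same way.
3. For other outcomes, keep all typed cases as the main analysis and add a sensitivity analysis limited to cases typed by DAA and fasting C-peptide.
4. In 8.1.2, state that biochemically typed cases are the reference when clinical items are evaluated, in line with 7.2(b).

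The cost is a change of wording plus one variable per case. Table 5-1 lists how the diagnosis was validated, not how type was assigned, so that variable has to be added; DAA and C-peptide are already collected. The defining-feature tests lose cases: leaving out 10–20% moves the overall detectable difference from 0.098 to about 0.103–0.109 SD. The loss among incident cases could be larger, and the protocol gives no figure for it. The report should also state that biochemical type 2 is itself selected on high C-peptide.

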8.1.4 Estimation of the clinical course

The clinical course of incident subjects will be estimated from longitudinal data collected once per year. The natural history and comparison between disease types will be estimated and tested using repeated measures analysis of covariance and mixed models³⁷. Maximum likelihood will be used to fit these models. This allows increased precision and minimizes bias associated with varying lengths of follow-up among participants.

8.2 SAMPLE SIZE AND POWER ANALYSES

The projected study sample sizes of prevalent and incident cases are 6,378 and 785 per year, respectively. The bases for these estimates are discussed in Section 4.1. This sample size will allow very good precision in estimating the overall prevalence (per 1000 subjects) with a 95% confidence interval (CI) that is + or – 2.5% of the estimate. It will also provide age, gender, and race/ethnicity specific estimates that have CIs of + or – 10% of the estimate for most race/ethnicities.

Table 6-1. Precision of Confidence Interval (CI) Estimates for Prevalence

		Estimated # of Cases	Denominator	Prevalence	Standard Error	95% CI as % estimate
Overall		6378	3,518,342	1.81	0.023	2.5%
Age	0-9	1624	1,758,692	0.92	0.023	4.9%
	10-19	4754	1,759,650	2.70	0.039	2.8%
Gender	Male	3219	1,709,171	1.83	0.116	22.1%
	Female	3218	1,709,171	1.83	0.116	22.1%
Race/ethn icity	NHW	4187	2,312,452	1.81	0.028	3.0%
	Black	704	322,968	2.18	0.082	7.4%
	Hispanic	756	395,230	1.91	0.070	7.1%
	Asian	336	254,480	1.32	0.072	10.7%
	PI	238	80,309	2.96	0.192	12.7%
	Native Am	157	152,903	1.03	0.082	15.6%

This sample size will allow the estimation of total and age, gender, or race/ethnicity specific incidence (per 10,000 subjects) for a given year with the following precision:

Table 6-2. Precision of Confidence Interval (CI) Estimates for Incidence

		Estimated # of Cases	Denominator	Incidence	Standard Error	95% CI as % estimate
Overall		785	5,072,988	1.55	0.057	7.0%
Age	0-9	303	2,533,318	1.20	0.069	11.2%
	10-19	482	2,539,670	1.90	0.086	8.9%
Gender	Male	412	2,536,494	1.64	0.081	9.9%
	Female	411	2,536,494	1.64	0.081	9.9%
Race/ethn icity	NHW	544	3,284,466	1.66	0.071	8.4%
	Black	106	672,587	1.58	0.153	19.0%
	Hispanic	72	549,501	1.31	0.154	23.1%
	Asian	25	301,875	0.83	0.166	39.2%
	PI	18	89,162	2.02	0.476	46.2%
	Native Am	20	175,397	1.14	0.255	43.8%

Distributions of continuous measures (e.g., measures of vascular disease, complications, and health care utilization) will be compared between type 1 and non-type 1 cases. Assuming that 75% of identified subjects will participate in the study; the study will be able to detect differences in terms of the standard deviation (SD) of the characteristic being considered between type 1s and non-type 1s in the overall and age, gender, or race/ethnicity specific prevalent populations:

Table 6-3. Standardized difference that can be detected between type 1s and non-type 1s

		# Type 1	# Type 2	Difference that can be detected (SD)	
				80% Power	90% Power
Overall		3736	1048	0.10	0.11
Age	0-9	1119	99	0.29	0.34
	10-19	2617	949	0.11	0.12
Gender	Male	1868	524	0.14	0.16
	Female	1868	524	0.14	0.16
Race/ethn icity	NHW	2764	376	0.15	0.18
	Black	383	145	0.27	0.32
	Hispanic	337	230	0.24	0.28
	Asian	124	128	0.35	0.41
	PI	128	51	0.46	0.54
	Native Am	0	118	-	-

SEARCH Protocol – Section 9
Data Management
Table of Contents

9. DATA MANAGEMENT.....	2
9.1. DATA ENTRY CERTIFICATION	2
9.2. DATA ENTRY	2
9.3. LOCAL TRACKING APPLICATION.....	2
9.4. EDIT CHECKS	2
9.5. PASSWORDS	2
9.6. SECURITY.....	3

9. Data Management

The Coordinating Center will develop and maintain the computerized data management system for SEARCH data. Use of the SEARCH data management system will be restricted to only those persons having access authority. In addition to data entry, SEARCH site-specific reports, e.g. recruitment goals, follow-up rates, will be available via the study's web site.

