There are two large Universities and several smaller colleges within our geographic area of interest which include: The University of South Carolina, South Carolina State University, Columbia College, Benedict College, Allen University, Claflin University, and Columbia International University.

Estimated number of prevalent cases

Table 6. Estimated number of prevalent cases by age and ethnicity.

Age Group	White, NH/L ¹	Black or African American NH/L ¹	Hispanic or Latino	Asian, NH/L ¹	Hawiiian or Pacific Islander, NH/L ¹	Nat Amer Alaskan Native, NH/L ¹	or other ² , NH/L ¹	Total ³
0-9 Years	46	40	1	0	0	0	0	87
10-19 Years	128	143	9	2	0	1	0	283
Total 0-19 years	174	183	10	2	0	1	0	370

¹ Not Hispanic or Latino

² Other, not Hispanic or Latino category, set to zero because of unavailability of rates

³ Total based on non-rounded numbers

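### Section 8.2 and Appendix V: the Table 6-1 gender rows are wrong, the ±10% sentence holds for only three of six race/ethnicity groups, and expected cases were rounded down cell by cell

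*Protocol*

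**What the plan says.** Section 8.2 opens with the totals: "The projected study sample sizes of prevalent and incident cases are 6,378 and 785 per year, respectively". It then claims overall prevalence "with a 95% confidence interval (CI) that is + or – 2.5% of the estimate", and for specific groups plus or minus "10% of the estimate for most race/ethnicities".

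Table 6-1 gives cases, denominator, prevalence per 1,000, standard error and half-width as a percentage of the estimate:

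- Overall: "6378 3,518,342 1.81 0.023 2.5" (the last figure is a percentage, as in the rows below).
- Male: "3219 1,709,171 1.83 0.116 22.1".
- Female: "3218 1,709,171 1.83 0.116 22.1".
- Asian: "336 254,480 1.32 0.072 10.7".
- Pacific Islander 12.7% and Native American 15.6%; non-Hispanic white, Black and Hispanic 3.0%, 7.4% and 7.1%.

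The case counts come from Appendix V (Tables V-1 to V-6), which multiplies literature rates by denominators for each center, age group and race/ethnicity. South Carolina's own section has parallel tables (its Tables 6 and 8) footnoted "Total based on non-rounded numbers".

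Colorado's section lists 3,712 Pacific Islander youth in the prevalence area (4.1.2) and 1,367 in the incidence area (4.1.3).

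**The concern.** Prevalence and incidence by age, gender and ethnicity is the first primary aim, and Section 8.2 is where the protocol states the precision expected for it. Two rows there cannot come from the counts beside them, and one summary sentence disagrees with the table it introduces. Section 4.2.2.4 says the expected incident counts serve to assess power and plan resources, so a systematic shortfall in them matters most where cells are small: type 2 incidence and the smaller ethnic groups.

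**Working it through.** **Formula.** Standard error = √(p(1−p)/N), which for rare disease is √cases / N. The 95% half-width as a percentage of the estimate is about 196/√cases.

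**Reproducing the plan.** Overall: √6,378 / 3,518,342 × 1,000 = 0.023, and 196/√6,378 = 2.45%, printed 2.5%. All nine non-gender rows of Table 6-1 reproduce. In Table 6-2 every non-gender percentage reproduces to within the last printed digit. The overall standard error there is printed as 0.057, but 785 cases give 0.055.

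**Gender rows, Table 6-1.**

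| Quantity | Printed | From the printed 3,219 / 1,709,171 |
|---|---|---|
| Rate per 1,000 | 1.83 | 1.88 |
| Standard error | 0.116 | 0.033 |
| Half-width | 22.1% | 196/√3,219 = 3.45% |

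- The printed values also disagree with each other: 1.96 × 0.116 / 1.83 = 12.4%.
- The denominators sum to 2 × 1,709,171 = 3,418,342, which is 100,000 short of 3,518,342. Half the overall figure is 1,759,171, and 3,219 / 1,759,171 gives the printed 1.83.
- The cases sum to 3,219 + 3,218 = 6,437, not 6,378. In Table 6-2 they sum to 412 + 411 = 823, not 785.
- Half of the Native American row (78.5 cases in about 76,451) gives a standard error of 0.116 and 196/√78.5 = 22.1%. A wrong cell reference is therefore likely, though this is inference.
- The Table 6-2 gender percentages are about right: 9.9% printed, 196/√412 = 9.7%.

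**The ±10% sentence.** Within 10%: 3.0, 7.4, 7.1. Outside: 10.7, 12.7, 15.6. That is three of six.

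**Rounding down in Appendix V.** Examples: Ohio, 10–19, non-Hispanic white, type 1: 2.2 × 249,921 / 1,000 = 549.83, printed 549. Hawaii, 10–19, Asian, type 2: 13.9 × 68,730 / 100,000 = 9.55, printed 9. Each of Tables V-1, V-2, V-4 and V-5 has 64 cells with a non-zero denominator, 256 in all. Every one equals the product rounded down; ordinary rounding matches only 147.

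| Count | Printed | Not rounded down |
|---|---|---|
| Prevalent, type 1 + type 2 | 4,981 + 1,397 = 6,378 | 5,010.9 + 1,429.2 = 6,440 |
| Incident per year, type 1 + type 2 | 621 + 164 = 785 | 644.2 + 188.5 = 833 |
| Asian incident | 25 (39.2%) | 33.4 (33.9%) |
| Pacific Islander incident | 18 (46.2%) | 23.2 (40.7%) |

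With the fuller counts, overall half-widths become 2.44% (prevalence) and 6.8% (incidence). Asian, Pacific Islander and Native American prevalence become 10.5%, 12.5% and 15.3%, still above 10%.

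Section 8.2 appears to mix the two sets. Half of 6,440 is 3,220, next to the printed 3,219 and 3,218, and 833 cases give √833 / 5,072,988 × 10,000 = 0.057, the overall standard error printed in Table 6-2.

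**Pacific Islander denominators.** Colorado's incidence area (the whole state and more reservations) contains its prevalence area (13 counties and some of those reservations), yet has fewer Pacific Islander youth: 1,367 against 3,712, both from the 2000 census. The prevalence figure is a quarter of the Asian figure: 14,848 / 3,712 = 4.00. The same ratio appears in California (59,458 / 14,864) and Seattle (72,369 / 18,092). Seattle's own Table 1 has only a combined Asian/Pacific Islander count: 19,884 + 23,143 = 43,027 at ages 0–9, of which 80% is 34,422, the Asian entry in Appendix V.

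**The case against.** The strongest reply is that these are mostly editorial slips. That largely stands:

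- Every non-gender percentage follows from the cases and denominator in its row. A reader might infer that the precision tables as a whole are unreliable; the arithmetic does not support that.
- The protocol elsewhere quotes about 6,350 and about 6,000 prevalent cases, so a 62-case loss is immaterial to prevalence planning. Rounding down is conservative, and no design decision turns on it.
- A reader might infer from 22.1% that sex-specific prevalence will be poorly estimated. The counts give 3.5%.
- The ±10% sentence misses narrowly for Asian youth, and the exact values sit directly beneath it.
- South Carolina's totals (370 and 192, against 361 and 183 in Appendix V) are imperfect support. Unrounded Appendix V inputs give about 190.6 incident cases for that center, and its table shows 30 African American cases at ages 0–9 where the rates give 195,522 × (9.5 + 5.0) / 100,000 = 28.4.

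A reader might also infer from the Colorado conflict a specific lower Pacific Islander case count, or that Asian and Pacific Islander results should be merged. Neither follows. The documents do not show which Colorado figure is right or give a Pacific Islander share for California or Seattle, and Section 8.1.1 plans the two groups separately. Colorado supplies only 6 of the 238 expected Pacific Islander prevalent cases and none of the incident ones.

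The reply does not remove the errors: two rows contradict their own inputs, the sentence contradicts its table, and the totals differ from the stated method by 1% and 6%.

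**Conclusion.** The point holds within these limits. The Table 6-1 gender half-width is overstated 6.4-fold (22.1% against 3.45%) and its standard error 3.5-fold (0.116 against 0.033). The ±10% sentence is true for three of six groups. Rounding down cuts expected prevalent cases by 62 and incident cases by about 48 a year; the unrounded type 2 incident total is about 15% above the printed one (188.5 against 164). Only the ±10% sentence overstates precision; the gender rows and the rounding understate it, so feasibility is not in question. Colorado's Pacific Islander figures cannot both be right.

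This rests on the rates and denominators printed in Appendix V, and on reading the ±10% sentence one factor at a time, as Table 6-1 is laid out. If it meant race/ethnicity within sex, halving the counts would push Black (196/√352 = 10.4%) and Hispanic (196/√378 = 10.1%) past 10% as well.

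**What to change.** Recompute Appendix V without rounding down, and reissue Tables 4-2, 4-3, 6-1 and 6-2 on one consistent total; other places that carry the totals should follow. On the fuller total each prevalence gender row is about 3,220 cases, denominator 1,759,171, 1.83 per 1,000, standard error 0.032, ±3.5%. Reword the Section 8.2 sentence to say that half-widths are within ±10% for three of six race/ethnicity groups and 10.5–15.3% for the others.

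Separately, reconcile Colorado's 3,712 and 1,367, and state that the Asian/Pacific Islander split used for California, Seattle and Colorado prevalence is an assumed 80:20.

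The cost is recalculation and corrected text, with no change to case finding, data collection or the planned reporting categories.
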